8. Significant active cardio- or cerebrovascular disease after review by PI
9. Pregnancy
10. Unable to read, understand, and sign the Informed Consent Form (ICF) and if applicable, an Authorization to Use and Disclose Protected Health Information form (consistent with Health Insurance Portability and Accountability Act of 1996 [HIPAA] legislation), communicate with the investigator, and understand and comply with protocol requirements.
11. Known history of hypoglycemia unawareness

G. Diabetes Education Curriculum and Education Session Process :

Companeros en Salud curriculum:⁴⁸ The DSMES curriculum entails 12, 1-hour weekly educational classes¹ that will be led by CDEs and health educators (Appendix Q1). Each class will last 60-90 minutes, depending on class size and discussion by participants. The intervention emphasizes ADA clinical goals for blood glucose, A1C, blood pressure, and lipids, and is designed to reduce risk factors associated with T2D complications by optimizing T2D self-management activities. Target behaviors include healthy eating, physical activity, blood glucose monitoring, medication adherence, problem-solving, healthy coping, communicating with one's healthcare team, asking for support from family and friends, taking an active role in individual healthcare, and understanding what kind of T2D care is needed.

The curriculum is written in a conversational tone in plain language so that materials can be read as scripted. This approach facilitates learning for participants with little formal education and ensures intervention fidelity. An instructor's manual will ensure that the facilitators use standard instructional content and methods to deliver information and activities. Group discussion, role-playing, problem-solving, and hands-on activities are included to encourage engagement and enhance learning.

Session	Topic
1	Glucose Balance
2	Diabetes Medications
3	Food
4	Diabetes Diets
5	Exercise
6	Heart
7	Cholesterol
8	Feet
9	Stress
10	Preventing Complications
11	Diabetes Team
12	Living Well with Diabetes

Sociocultural strategies, which present T2D in the context of cultural values and community characteristics, are incorporated to increase the intervention's salience to participants. For example, a facilitator might begin a class with a story about ordinary community members with T2D, using culturally relevant metaphors to link their situation with effective self-management behaviors. At the end of each class a survey will be given to the participants for each session (Appendix Q2)

All educational classes will be conducted via the Zoom platform for telemedicine or in person at Sea mar classroom per patient preference in group setting. Zoom education sessions will be recorded and the zoom platform announces the session will be recorded prior to you joining the meeting. Session recordings will not be used for research but only to allow you or participants to watch the recorded session if you miss the live education session. It is highly encouraged to attend all sessions live for maximum education opportunity. Patient Navigators from Sea Mar will act as digital navigators and, prior to first session through first home visit as detailed below, will ensure participants have working devices for classes and if needed will provide hot spot for the class. PN will be available for problem shooting for joining the sessions via telephone and if more than 2 sessions missed and no response from participants, PN will have option of second home visit to check on participant and any barrier for attendance.

Participants will receive a telephone and or text and or email reminder 24 hours before each scheduled intervention class. Participants will send their name and may only use their first name or pseudonym if preferred through the chat feature on Zoom to track attendance. At the conclusion of each class, participants will be asked to set a goal related to the presented topic and will complete a brief satisfaction questionnaire. At each subsequent class, the facilitator will ask participants to discuss their successes and challenges in achieving their goals. For participants who miss a class, study staff will make up to 2 telephone calls to check in and confirm attendance for the next session. If 3 or more people miss a class, the facilitator will try to schedule a make-up class before the next scheduled session. If fewer than 3 people miss the class, or if it is not possible to schedule a make-up session, materials for the missed class will be available as recording but live attendance via Zoom will be stressed. People who miss 4 consecutive classes or a total of 8 total classes will be considered dropouts. However, these participants will not be turned away from future sessions if they decide to attend. All participants will always be included in follow-up data collection, regardless of class attendance or retention.

H. Study Design

Screening: Interested volunteers will be pre-screened by telephone or in person in respective clinics or via televisit and then scheduled for a screening visit (week 0). If potential participants express interest, they will be provided an email address or phone number to call for more information.

Alternatively, participants will be asked if they would like to be called to receive more information and are willing to provide their contact information to study staff. If after receiving more information, the potential participant is interested, then pre-screening questions (appendix C) will be asked. If still eligible, then a screening appointment will be arranged by study staff. If the participant is not interested in participating, the participant will continue standard diabetes care with their primary care clinic .

Study visits and intervention:

Baseline Visit/Visit 1. Base line visit is 2-4 weeks prior to Week 1, which is the start of education intervention. Week 1 is the first week of the education sessions. Baseline visit will occur in the participant's home or at a local Sea Mar clinic and/ or maybe a combination of remote and in-person. A research coordinator will review the full informed consent document, explaining study goals, procedures, and any potential risks in Spanish or English. Consent (appendix Z ?) will be obtained prior to any screening procedures being completed, and conducted in a quiet room or private televisit. Participant will be given ample time to ask questions, and a copy of the signed consent form will be given prior to start of screening visit procedures. Participants will fill out a contact form, including emergency contact (appendix Z1). Study staff will review medical history and medications and family history (appendix D), as well as all inclusion/exclusion criteria. Point of care A1C will be measured via point of care testing with a Siemens DCA Vantage A1C Analyzer, at LabCorp or quest for serum A1C if remote visit is completed. All women of child-bearing potential will undergo a urine pregnancy test either point of care or at LabCorp. Participants who meet criteria for enrollment and wish to proceed with study participation will be randomized to an intervention arm in unblinded fashion.

Remote Consent : If baseline visit is remote/virtual, the consent form will be sent to the participant via REDCap to be viewed and signed remotely. Subjects can also request that a paper copy of the consent be mailed to them before Visit 1. The informed consent discussion includes time for the potential participant to read over the consent form and to think about their questions. If the potential participant has questions outside of the Research Coordinator's scope, the potential participant will be offered a follow-up consultation with the Principal Investigator or Co-Investigator who can provide more information. As this is a minimal risk study, we will request a waiver of documentation of consent.

Randomization. The study biostatistician will generate a randomized sequence of treatment group assignments using stratified permuted-block randomization (random block sizes of 2, 4, 6) stratified by A1C >9.0% and ≤9.0%. Sequences will be stored at and delivered through the REDCAP study database at the UW. Research staff will obtain the next randomization once a potential study participant has been determined to be eligible and has signed the study consent form.

Vital signs, anthropometrics measurements, and demographic information will be collected, and participants will be asked to complete study surveys as further detailed below. Participants will be asked to use pedometers and keep them on their person as much as possible during waking hours. Baseline data will be collected no more than 3 weeks prior to the initiation of the DSMES curriculum, and pedometer data will be collected over 10 days immediately following the baseline study visit. Both groups will undergo blinded CGM with insertion by study personnel over the same 10 days following the baseline visit. Participants will then have a follow up visit from a Patient Navigator 10-14 days after the initial visit (detailed below) If less than 72 hours of CGM data is obtained at follow up PN visit participants will be asked to repeat blinded CGM. Participants will be asked to continue their customary dietary and exercise habits until initiation of the intervention

Follow-up study visits given in a community setting will be within an acceptable window for data collection and held at weeks 12+/-2 weeks and 24+/-2 weeks (Visits 2: end of education intervention and visit 3:12 weeks after education intervention. The same procedures will be completed as described in detail below. Visits 2 and 3 also may be held in the participant's home or Sea Mar clinic according to the participant's preference and be completed through a remote RC visit with a PN in person visit to complete blood pressure, weight circumference and weight and A1c. The study team will continue to contact withdrawn participants to conduct an interview regarding barriers to study engagement.

Study Procedures

The following procedures will be performed at baseline (visit 1), (Visit 2) and (Visit 3):

Anthropometric and vital sign measurements: **Height** will be measured by a Stadiometer. **Weight** will be measured using a SECA Digital scale, and BMI (kg/m^2) will be calculated. **Waist circumference** will be measured using a flexible measuring tape. Participants will remain in a seated position for a minimum of 15 minutes prior to measurement of **resting heart rate** and **blood pressure** with an Omron Professional Digital blood pressure and heart rate monitor.

Concomitant medications: Participants will be instructed to bring all current medications (prescription, over the counter, and herbal or vitamin supplements) to each study visit. The research study coordinator will review and record these medications. Comorbidities: We will use patient self-report to document stroke, CVD (congestive heart failure, myocardial infarction, or coronary heart disease), peripheral vascular disease, peripheral neuropathy, renal disease, and retinopathy. Point of Care A1C: The DCA Vantage Analyzer tests for a quantitative determination of A1C in human whole blood and provides immediate test results from a finger prick of blood. If age <50 and female urine dipstick for pregnancy completed.

Pedometer: participants will be given a pedometer or if preferred use the one available on their smartphone. They will be asked to keep the pedometer or phone on them as much as possible during waking hours during the study. Data will be collected for 10 days after the first visit then for the 10 days prior for visits 2 and 3.

Continuous Glucose Monitoring:

Blinded CGM: All participants will undergo blinded CGM for 10 days at baseline a (2-4 weeks prior to start of education) and visit 3 (24 weeks [+/-2 weeks]). The blinded CGM- education group will also complete blinded CGM for 10-day period at the end of the education intervention (visit 2: study weeks12 [+/-2 weeks]). Participants can mail blinded CGM devices back in self-addressed postage-paid envelopes provided at the initial PN visit and devices will be provided at the first PN visit.

RT-CGM: Participants in the RT-CGM arm will be asked to wear the device for a total of 50 days for 84 days during the 12 weeks of education sessions at intervals of 10 days on then 7 days off over 12 weeks. CGM data for 10 days will be downloaded after the completion of the 3rd RT-CGM wear session which should correlate approximately with the 6th education session. The final period of RT-CGM use will begin on the day of the final session of the DSMES curriculum. Participants will undergo initial training by PN and can have assistance for the first device self-insertion and may request additional virtual, telephone, or in-person assistance from PN. In our experience, study participants readily assimilate the self-insertion technique and require negligible follow-up support for this procedure. RT-CGM data will be collected remotely using a cloud-based platform

Preparation for the study intervention: Patient Navigators (PN) from Sea mar health education team will engage participants no more than 2-4 weeks prior to the start of the DSMES intervention to ensure participants have a working technology platform for the education sessions and provide hot spot if able through one home visit with option for second if need to assess barriers to technology or attendance. For all participants, PN will teach simple CGM insertion (blinded and RT). For those who are enrolled in RT-CGM arm, the PN will set up a mobile app for the RT-CGM device. PN also will conduct a 1, 30-minute training session on CGM for participants in this study, with particular focus on the use of RT-CGM as a tool to understand food and activity choices. If RC is remote PN may also engage at visits 1, 2 and 3 to gather objective measurements (weight, blood pressure and POC A1C or participant may go to LabCorp/quest for the A1C) As well they well gather the 10 days baseline pedometer data

Study Procedures: Study Participants' Household Member: No protected health information will be recorded for household member. Demographics of relationship to study participant, age and sex and history of diabetes or prediabetes will be recorded at baseline visit. Email address maybe recorded in order to contact patients if verbal permission is given.

For both groups, at baseline (visit 1), visit 2 and 3 any available household members with minimum age 8 will be asked to complete two short questionnaires about nutrition and activity for those age ≥ 13 the starting the conversation and physical activity questionnaire that the participant was given will be used. For those household members 8-<13 the Habits questionnaire about lifestyle that has been validated for children will be used. After visit one and visit two, household members of the RT-CGM education group whom are over 13 years of age will also be asked to complete a short questionnaire. The questionnaire asks whether they are aware of the CGM in the household and if it influenced lifestyle changes.

[figure not shown]

Figure 1: Study Design Schematic: N=100 Control N=50 (Blind-CGM-Education group) and Intervention group (RT-CGM-Education) N=50

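### No available text withholds the arm until the 10-day baseline CGM and step recordings have ended

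*Combined protocol and SAP*

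**What the plan says.** Section H, Baseline Visit/Visit 1, runs through consent, eligibility review, A1C and pregnancy test, and ends with participants who "will be randomized to an intervention arm in unblinded fashion". The Randomization paragraph gives the trigger: "Research staff will obtain the next randomization once a potential study participant has been determined to be eligible" and consent has been signed. Completing the baseline recordings is not a condition.

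The same section then describes the recordings. For steps, "pedometer data will be collected over 10 days immediately following the baseline study visit". For glucose, "Both groups will undergo blinded CGM with insertion by study personnel over the same 10 days following the baseline visit". Next, "Participants will then have a follow up visit from a Patient Navigator 10-14 days after the initial visit", and "If less than 72 hours of CGM data is obtained at follow up PN visit participants will be asked to repeat blinded CGM". The only instruction on behaviour in this period is "Participants will be asked to continue their customary dietary and exercise habits until initiation of the intervention".

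The baselines are then used as follows:
- Section N bases between-group CGM comparisons on change from baseline to weeks 12 and 24.
- The pedometer text in section K compares follow-up steps with baseline steps.
- The Data Analysis Plan for Aims 3 and 3A lists steps/day as a secondary outcome and codes the RT-CGM coefficient as a difference in 12-week change.
- The Data Analysis Plan for Aim 1 gives TIR two treatments: descriptive statistics for between-group differences, and a mixed model.

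**The concern.** Masking the CGM display hides glucose readings. It does not hide the arm. If participants learn their arm at visit 1, the two arms may eat, move or wear devices differently during a period that the analysis treats as pre-intervention. The protocol's Preliminary Studies section itself expects RT-CGM to work through diet and activity, which steps and CGM measures would reflect.

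Randomisation protects a baseline only if it is recorded before allocation can influence it. A baseline affected by knowledge of the arm cannot be repaired afterwards, and it enters directly into the change-from-baseline contrasts for steps/day and the CGM measures.

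**Working it through.** The plan states no figure on this point, so there is none to reproduce. The check is a reading of the sequence, then a short calculation under stated assumptions.

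**1. Order of events.** Randomisation sits within visit 1. Both recordings start after visit 1 and last 10 days. No readable text ties allocation or disclosure to their end. When A1C comes from an outside laboratory, allocation may fall later, but still without any link to the recordings.

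**2. Signs of early knowledge.** Under CGM Ancillary Devices, each participant's CLARITY account uses a study number issued at randomisation. Section S builds the group initials into that number (DMC or DMCGM). Under Preparation for the study intervention, the navigator sets up the RT-CGM app for that arm only. If that is the day 10-14 visit, a repeat baseline wear arranged there could follow arm-specific set-up.

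**3. Outcomes exposed.**
- Steps/day: exposed, because the contrast is a difference in change.
- CGM measures: exposed as estimates. For TIR, whether a between-arm test is planned is unclear.
- Visit-1 surveys: exposed only if completed after allocation, and then only through reporting, since the diet questionnaire asks about the past week.
- A1C: not exposed. It decides eligibility and the randomisation stratum, so it is measured before allocation.

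**4. Direction of bias.** Let D = (F_R - B_R) - (F_C - B_C), where F is follow-up, B is baseline, R is RT-CGM and C is control. If knowing the arm moves B_R by s and nothing else, D moves by -s. If F_R moves by s as well, D is unchanged.

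**5. Illustration.** The inputs are n = 85 after 15% attrition (Sample Size Estimation), taken as 42 and 43 per arm, two-sided 5%, and no true effect. The shift s is an assumption, in units of the SD of change.

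SE = sqrt(1/42 + 1/43) = 0.217.

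Error = Phi(s/SE - 1.96) + Phi(-s/SE - 1.96).

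| Baseline-only shift s | Calculation | Two-sided error |
|---|---|---|
| 0.1 | 0.067 + 0.008 | 7.5% |
| 0.2 | 0.150 + 0.002 | 15% |
| 0.3 | 0.282 + 0.0004 | 28% |

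For a shift that persists unchanged to follow-up, the bias is zero and the error stays at 5%. If a baseline-adjusted model were used instead (equal SDs, baseline to follow-up correlation r), the bias would be r x s in size for a baseline-only shift and (1 - r) x s for a persistent one. With s = 0.2 and r = 0.5 to 0.7 (values borrowed from the plan's A1C assumptions), the error would be 8.3% to 10.8% and 8.3% to 6.0% respectively.

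**6. Room in the schedule for later release.** Days left = lead time from visit 1 to Week 1, minus 10 to 14. A repeat wear takes 10 more.

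| Visit 1 before Week 1 | Days left after navigator visit | After a repeat wear |
|---|---|---|
| 14 days | 0 to 4 | does not fit |
| 21 days | 7 to 11 | fits only if the visit is on day 10 or 11 |
| 28 days | 14 to 18 | 4 to 8 days left |

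The 28-day row depends on how the visit-1 window is reconciled with "Baseline data will be collected no more than 3 weeks prior to the initiation of the DSMES curriculum". Aim 1 puts baseline at 0-4 weeks. With visit 1 less than 10 days ahead, the recordings would still be running when classes begin.

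**The case against.** The strongest reply is that the documents never say the participant is told the arm at visit 1. Figure 1 is not shown, and Appendix B, the measurement table, is listed but not available; either might give a different order. That stands, and it limits the claim to what the available text fails to prevent. A reader might infer that all baselines are recorded with the arm known. The documents do not establish that.

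Second, there are real mitigations. Readings are masked in both arms, both arms attend the same classes, and usual habits are requested until the intervention starts. These reduce the risk, but none conceals the arm.

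Third, the error rates rest on assumed shifts confined to baseline. In an open-label trial the arm is also known at follow-up, and a persistent shift cancels in a change score. This stands: the figures show sensitivity and do not estimate what will happen.

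Fourth, a reader might infer that a planned between-arm test of TIR is invalid, or that sugared-beverage consumption, the Aim 3 primary outcome, is compromised. Neither follows. The TIR analysis is described in two ways, and section M says only that the questionnaires are completed at the baseline visit, without placing them after allocation.

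Fifth, holding the allocation through a repeat wear needs a later set-up contact. That is correct, although section T already provides for unscheduled visits when CGM data are lacking.

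**Conclusion.** The point holds as a low-cost improvement. The available text allows the arm to be known during the baseline recordings and contains nothing to stop it. The clearest exposure is the between-arm change in steps/day, followed by the CGM measures as estimates. Survey exposure is conditional on their order and limited to reporting.

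The size and direction of any shift cannot be learned from the documents, so no error rate can be attributed to the trial. The 15% figure requires a shift of 0.2 SD of change that is absent at follow-up, 42-43 per arm and a change-score contrast. It would be wrong to read this as a threat to the primary result: baseline A1C precedes allocation, and the whole-cohort Aim 1 inference does not compare arms.

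**What to change.** Amend section H as follows:
1. Complete all visit-1 surveys and measurements before the allocation is opened.
2. Open and disclose the allocation only after the 10-day baseline CGM and step recordings, at the existing day 10-14 Patient Navigator visit and before any RT-CGM set-up or training.
3. Where a repeat wear is needed, hold release until it ends if the schedule allows. Otherwise record the disclosure date, flag that baseline as post-allocation, and examine it in a sensitivity analysis.
4. Issue arm-neutral study and CLARITY numbers at consent.

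Reconcile these passages first:
- Baseline timing: 0-4 weeks in Aim 1, 2-4 weeks before Week 1 under Baseline Visit/Visit 1, and the 3-week cap under Randomization.
- The repeat-wear trigger: any recording under 72 hours under Randomization, but device malfunction only under Medical Devices.
- When baseline devices are returned and read: at the navigator visit under Randomization, but mailed or handed in at the first education session under Medical Devices.

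The cost is a protocol amendment with no additional participants. RT-CGM supplies are assigned later and the lead-in to Week 1 is tighter. Participants who repeat the wear need a later set-up contact. Section S limits REDCap access to database coordinators and study staff, so either a coordinator releases the allocation or navigators are given access.
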